7.9.2.4 Sample Size justification

The sample size was estimated using a one-sided test ($\alpha=0.0125$) for one mean (PASS 2011 module Tests for One Mean) to compare the difference in aDBS TEED to cDBS TEED of 22 and a standard deviation of 35, a minimum of 36 subjects achieves at least 90% power.

Based on the registry data and the bench testing, a conservative estimate based on the first quartile of TEED data for initial devices in the registry, TEED is expected to decrease 35 and 22 units for aDBS single threshold mode and aDBS dual threshold mode, respectively. A SD of 36 results in a medium to large effect size of 0.629.

7.9.2.5 Analysis methods

The secondary analysis will use the FAS Analysis Set as described in section 7.1.3. Change in TEED will be used to evaluate the secondary objective. A paired t-test will be used to compare the difference in TEED for each aDBS mode (Evaluation Phase) to cDBS (Baseline Phase), separately. Normality of the outcome will be assessed with the Shapiro-Wilk test. If large violations to the normality assumption are observed ($p<0.05$), the primary analysis will use a Wilcoxon signed-rank test to assess statistical significance.

7.9.2.6 Handling of missing data

All attempts will be made to minimize missing data. If 5% of the data or fewer are missing for the analysis, no imputation will be used and the data will be analyzed as specified in the previous section. Otherwise, if missing data are observed, multiple imputation will be used for the analysis of the secondary objective.

Prior to the MI, the distribution of the continuous variables will be assessed for normality (using the Shapiro-Wilk test) to determine whether regression ($P \geq 0.05$) or predictive mean matching ($P < 0.05$) multiple imputation will be used for each variable. First, multiple imputation will be applied to impute missing values in TEED for each mode separately (aDBS single threshold, aDBS dual threshold). The model variables to include and methods used for the MI analysis are described in Section 7.9.1.5, except that a variable for cDBS TEED will be included in the model instead of cDBS hours of "On" time without troublesome dyskinesia. The FCS method within SAS (version 9.4 or higher) with 5 repetitions and 100 burn-in iterations will be used for imputation. No limits will be defined for imputed values.

Following imputation, the mean and standard error of the change in TEED will be determined for each imputation using Proc UNIVARIATE:

Proc MIANALYZE will be used to combine the summary statistics and to test the change in TEED with a t-statistic comparing the value to no change.

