13.5.4. Sample Size justification

The sample size was estimated using a one-sided test (alpha=0.0125) for one mean (PASS 2011 module Tests for One Mean) to compare the difference in aDBS TEED to cDBS TEED of 22 and a standard deviation of 35, a minimum of 36 subjects achieves at least 90% power.

Based on the registry data and the bench testing, a conservative estimate based on the first quartile of TEED data for initial devices in the registry, TEED is expected to decrease 35 and 22 units for aDBS single threshold mode and aDBS dual threshold mode, respectively. A SD of 36 results in a medium to large effect size of 0.629.

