13.5.6. Handling of missing data

All attempts will be made to minimize missing data. If 5% of the data or fewer are missing for the analysis, no imputation will be used and the data will be analyzed as specified in the previous section. Otherwise, if missing data are observed, multiple imputation will be used for the analysis of the secondary objective.

Prior to the MI, the distribution of the continuous variables will be assessed for normality (using the Shapiro-Wilk test) to determine whether regression ($P \geq 0.05$) or predictive mean matching ($P < 0.05$)

Medtronic Business Restricted

multiple imputation will be used for each variable. First, multiple imputation will be applied to impute missing values in TEED for each mode separately (aDBS single threshold, aDBS dual threshold). Variables for target site (STN or GPi) and cDBS TEED will be included in the model. The fully conditional specification (FCS) method within SAS (version 9.4 or higher) with 5 repetitions and 100 burn-in iterations will be used for imputation. No limits will be defined for imputed values. Following imputation, the mean and standard error of the change in TEED will be determined for each imputation and combined using MI analysis and tested with a t-statistic comparing the value to no change.

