Since the device implant will occur outside of the study and the study requires participants to be stable on cDBS prior to enrollment, the standard deviation of the change from cDBS to aDBS in “On” time

without troublesome dyskinesia will be used to establish a threshold for assessing the performance goal. The threshold will be set as 1 standard deviation. If the difference between aDBS and cDBS (aDBS-cDBS) for a subject is at least -1 standard deviation, the threshold will be met for the subject. Using this threshold, the proportion of subjects who exceed the threshold will be computed.

The sample size was estimated using a binomial distribution for a one-sided exact test (alpha=0.0125) for a proportion (PASS 2011 module Tests for One Proportion [Differences]) to compare to a performance goal of 50%. Assuming the alternative hypothesis of 85% of subjects exceeding the threshold, a minimum of 36 subjects achieves at least 90% power to reject a performance goal of 50%.

Simulations have shown that this sample size is sufficient to cover possible deviations from normality such as a uniform distribution. The threshold criterion will remain the same as the standard deviation is robust to moderate departures from normality.

Sample size in the Primary Cohort may be increased to a maximum of 55 subjects for whom at least 1 aDBS mode is acceptable and who enter the aDBS Evaluation Phase to obtain at least 8 subjects per aDBS mode and 8 subjects per target site (Subthalamic Nucleus [STN]/ Globus Pallidus [GPi]). Criteria for increasing sample size is described in section 7.2.1.

For the safety analyses, a minimum of 30 subjects followed for approximately 30 days with aDBS out-of-clinic in the subjects' real-world environments provides at least 95% probability that all events with a true event rate of at least 10% would be reported at least once.

It is estimated that approximately 70-100 subjects implanted with a commercially available Medtronic DBS system with Percept PC INS will be enrolled in the study to obtain 40 subjects for whom at least 1 aDBS mode is acceptable and who enter the aDBS Evaluation Phase. Accounting for a 10% dropout during the aDBS Evaluation Phase, a minimum of 36 subjects (at least 8 per brain target site (STN/GPi) and 8 per aDBS mode) will complete the aDBS Evaluation phase.

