7.5 Adjustments for Multiple Comparisons

In the Primary Cohort, the familywise error rate will be controlled using one-sided tests with an overall alpha-level of 0.025. Each primary hypothesis (one for each aDBS mode) will be assigned a Bonferroni corrected alpha (0.0125) for the respective primary hypothesis (0.025/2). The primary hypothesis will serve as a gatekeeper for the secondary hypothesis within each mode. No adjustments of multiple comparisons are needed for the Directional Stimulation Cohort as no hypothesis testing will be conducted.

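### The degrees of freedom of the multiply imputed TEED t-test are not stated; under the cited Rubin rule its one-sided size is about 0.015, not 0.0125

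*SAP*

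**What the plan says.** TEED is the confirmatory secondary endpoint, tested separately for each adaptive mode. SAP 7.5 splits the one-sided 0.025 into 0.0125 per mode and adds that "The primary hypothesis will serve as a gatekeeper for the secondary hypothesis within each mode". The level is repeated in Protocol 13.5.4: "The sample size was estimated using a one-sided test (alpha=0.0125) for one mean (PASS 2011 module Tests for One Mean".

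The analysis has two branches.

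- **5% or less missing.** SAP 7.9.2.5: "A paired t-test will be used to compare the difference in TEED for each aDBS mode". This test has n − 1 degrees of freedom. If the Shapiro-Wilk test rejects normality, a signed-rank test replaces it.
- **More than 5% missing.** SAP 7.9.2.6 imputes five times by fully conditional specification and takes the mean and standard error of the change from each imputed dataset with Proc UNIVARIATE. Then "Proc MIANALYZE will be used to combine the summary statistics and to test the change in TEED with a t-statistic". Protocol 13.5.6 says the results are "combined using MI analysis and tested with a t-statistic comparing the value to no change".

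The readable text of neither section gives the degrees of freedom for the second branch. The references for combining imputations in SAP 7.4 and Protocol 13.2.5 are Rubin 1976 and 1987. In the public SAP, the Proc UNIVARIATE sentence ends in a colon with nothing after it, and the version log records that example code for the imputation analyses was added. Code may therefore stand there in the full document.

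**The concern.** The Rubin (1987) degrees of freedom depend only on the number of imputations and on the ratio of between- to within-imputation variance. They treat the complete-data variance as known. With few missing values that ratio is small, so the degrees of freedom become very large and the critical value moves towards the normal one, although the variance is estimated from only a few dozen subjects.

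Two things would follow. The test would exceed its allotted one-sided 0.0125. It would also be easier to pass with some TEED values missing than with none missing, which is the wrong direction. And because the prose leaves the choice open, two analysts could report different p-values for the same confirmatory test.

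**Working it through.** **Inputs from the documents.** One-sided alpha 0.0125 per mode (Protocol 13.5.4, SAP 7.5). Difference 22, SD 35, N 36, power at least 90% (SAP 7.9.2.4). Five imputations and a 5% trigger (SAP 7.9.2.6). 40 subjects entering and 36 completing (SAP section 6). Per-mode analysis down to 24 subjects, because SAP 7.2.1 uses first-period data from all subjects when fewer than 24 are programmed to a mode for unacceptability.

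**Assumptions not in the documents.** aDBS TEED values missing completely at random; correlation between aDBS and cDBS TEED 0.5 or 0.8; one quarter of subjects in one target site; normal data; regression imputation on cDBS TEED and target site; no complete-data degrees of freedom supplied to the combining step.

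**The plan's own figure.** SAP 7.9.2.4 gives "TEED of 22 and a standard deviation of 35, a minimum of 36 subjects achieves at least 90% power".

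- Noncentrality = (22/35) × √36 = 0.6286 × 6 = 3.771.
- The critical value of t with 35 df at one-sided 0.0125 is 2.342.
- Power from the noncentral t is 0.918, so the statement reproduces.

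The same section also says "A SD of 36 results in a medium to large effect size of 0.629". But 22/36 = 0.611, and 0.629 is 22/35. With SD 36, power at N = 36 is 0.902, so the sample size holds either way.

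**Which counts trigger imputation.** At n = 36, one missing is 1/36 = 2.8% (no) and two is 2/36 = 5.6% (yes). At n = 40, two is exactly 5.0% (no) and three is 7.5% (yes). At n = 24, two is 8.3% (yes).

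**Degrees of freedom, worked example.** Let r be the relative increase in variance from missing data and λ = r/(1 + r). With m = 5, λ = 0.10 and complete-data df ν₀ = 35:

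- Rubin: (m − 1)(1 + 1/r)² = 4/λ² = 4/0.01 = 400. Critical value 2.250.
- Barnard-Rubin: the observed-data term is (1 − λ)ν₀(ν₀ + 1)/(ν₀ + 3) = 0.9 × 35 × 36/38 = 29.84. Then df = 1/(1/400 + 1/29.84) = 27.8. Critical value 2.370.
- For comparison, complete data (t with 35 df) give 2.342 and the normal gives 2.241.

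The Rubin cut-off thus lies below the complete-data cut-off, and the Barnard-Rubin cut-off lies above it.

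**Limiting size if the normal cut-off is used on a t-statistic.** P(t₃₉ > 2.241) = 0.0154; P(t₃₅ > 2.241) = 0.0157; P(t₂₃ > 2.241) = 0.0175.

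**Simulated one-sided size at nominal 0.0125** (null data, both tails counted and halved, 1,000,000 runs per row):

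| n | missing | correlation | median Rubin df | size, Rubin df | size, df from n − 1 |
|---|---|---|---|---|---|
| 36 | 2 | 0.5 | 1831 | 0.0152 | 0.0118 |
| 36 | 4 | 0.5 | 450 | 0.0150 | 0.0115 |
| 36 | 4 | 0.8 | 326 | 0.0153 | 0.0116 |
| 40 | 4 | 0.8 | 409 | 0.0151 | 0.0118 |
| 36 | 7 | 0.8 | 107 | 0.0147 | 0.0110 |
| 24 | 2 | 0.8 | 522 | 0.0165 | 0.0110 |

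A shorter run with n = 24 and 3 missing gave 0.0168, and a separate simulation with n = 24 and 2 missing gave 0.0172.

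**What the shift means at the design effect.** With noncentrality 3.771 and 35 df, the chance that the statistic falls between 2.250 and 2.342 is about 1.3%.

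**The case against.** The strongest objection is that the plan may already be right. The public text breaks off where code would stand, and what is absent for that reason cannot be counted as missing from the plan. A reader might infer that the test is run without complete-data degrees of freedom; the documents do not show that. What Proc MIANALYZE does when none are supplied is also a software assumption, not a statement in either document. This objection stands, and it makes the point conditional. It does not remove it: the version log describes the code as examples that could be used, which would not bind the analysis, and Protocol 13.5.6 reads as complete prose and also leaves the choice open.

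Three stronger readings are tempting and are not supported.

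- *That imputation is the likely branch.* The allowance "Accounting for a 10% dropout during the aDBS Evaluation Phase" is twice the 5% trigger, but it is a sample-size allowance and not a forecast of missing TEED. A randomized subject who leaves in the second period has already contributed the first mode. TEED comes from device files, and SAP 7.9.2.3.3 provides a fallback for missing impedance.
- *That the error over both modes reaches 0.03.* This is only the bound 2 × 0.015. Both changes subtract the same subject's cDBS value, so the tests are correlated. With bivariate normal statistics at 0.0152 each, the joint error is 0.028, 0.026 and 0.024 at assumed correlations of 0.5, 0.7 and 0.8; the last is below 0.025.
- *That the test is in effect a z-test throughout.* This fits low missingness. At 7 of 36 missing, median df is already down to about 107.

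It is also fair to say that the effect is small and that SAP 7.9.2.7 plans complete-case and as-treated analyses without imputation. Under normality the complete-case test uses n − 1 degrees of freedom, so a result that turned on this choice should be visible.

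**Conclusion.** The point holds in conditional form and is minor. The readable text does not state the degrees of freedom for the imputed TEED test. If the cited Rubin (1987) rule is followed as it stands, one-sided size is about 0.015 at n = 36 to 40, an excess of roughly 0.2 to 0.3 percentage points over 0.0125. It is about 0.017 at n = 24, the floor for per-mode analysis. The test is then slightly more lenient than the paired t-test it replaces.

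This rests on more than 5% of data being missing, on code that does not already supply complete-data degrees of freedom, and on normal data with regression imputation. The predictive mean matching branch, used when Shapiro-Wilk rejects normality, was not checked. At the design effect the choice would seldom change the conclusion.

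**What to change.** Add one sentence to SAP 7.9.2.6 and Protocol 13.5.6: Proc MIANALYZE is run with EDF equal to the number of subjects analysed in that mode minus 1, giving Barnard-Rubin degrees of freedom, and the one-sided p-value is compared with 0.0125.

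The cost is one option in the code and one sentence per document. Simulated size becomes about 0.011 to 0.012, so the test is slightly conservative. If the code already does this, the sentence only puts it on record.

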7.9.2.7 Supporting analyses

Supporting analyses for the secondary objective in the Primary Cohort include verifying the lack of a period or carryover effect (randomized subjects only), tests for poolability by target site (STN/GPi), tests for poolability by lead type (legacy Models 3387 and 3389 compared to SenSight Models B33005 and B33015), and tests for poolability by center. The test for a carryover effect will use a two-sample t-test,

all other supporting analysis tests will use linear regression models. In addition, results from the Directional Stimulation Cohort will be described as a supportive analysis. The test of no period or carryover effect will be computed first, and if the assumption of no period or carryover effect is accepted, data from both periods from all subjects treated with aDBS in the aDBS Evaluation Phase will be used for the models to assess poolability by target site, lead type, and center. The models will use the change between aDBS and cDBS and include an intercept and a covariate for the respective parameter.

If the P-value is >0.1 , that will be deemed as supporting the assumption of no carryover effect and data from both periods from all subjects treated with aDBS in the aDBS Evaluation Phase will be used for the models to assess poolability by target site, lead type, and center. If a carryover effect exists (P-value ≤ 0.1), only data from the first period will be used for the analysis.

The tests for poolability of target site (STN/GPi), lead type, and center will be performed, by mode, and will include all subjects who enter the aDBS evaluation phase.

P-values >0.1 for the terms testing the effect of the respective parameters will be deemed as supporting the assumption of no target site effect, lead type effect, or center effect, respectively, and the data will be considered poolable across the respective variable. Normality of the outcome will be assessed with the Shapiro-Wilk test. If large violations to the normality assumption are observed ($p<0.05$), the

secondary endpoint may be transformed (e.g., log-transformation) or apply non-parametric method for the supporting analyses.

In addition, sensitivity analyses will be conducted using the CC and AT Analysis Sets without imputation.

7.9.3 Additional Objectives

To characterize each aDBS mode as compared to cDBS, the additional objectives described in sections 7.9.3.1 through 7.9.3.9 will be evaluated separately for each aDBS mode. The additional objectives in section 7.9.3.10 through 7.9.3.11 will characterize each aDBS mode, separately, without comparisons to cDBS. Additional objectives will be characterized for the CC unless otherwise specified, and the subgroup analyses described in section 4.4 will be performed on the CC analysis set and DSAT combined. Relevant references for additional objectives can be found in the study CIP.

Summary statistics may be presented for continuous measures (e.g., N, means, medians, standard deviations, minimums and maximums) and categorical measures (e.g., N, percentage, frequency distributions) with 95% confidence intervals as appropriate. If performed, missing data imputations will be conducted as specified within the respective sections. No adjustment will be made for multiple testing as no hypothesis testing will be conducted for the additional objectives.

To characterize aDBS as compared to cDBS for the objectives in sections 7.9.3.1 through 7.9.3.7, summary statistics will be provided in each aDBS mode and in cDBS along with the difference in aDBS and cDBS for continuous objectives. The difference will be calculated as follows for outcomes in which higher values are better:

$$\Delta_{\text{aDBS dual threshold mode}} = \theta_{\text{aDBS dual threshold mode}} - \theta_{\text{cDBS}}$$

and

$$\Delta_{\text{aDBS single threshold mode}} = \theta_{\text{aDBS single threshold mode}} - \theta_{\text{cDBS}}$$

And as follows for outcomes in which lower values are better:

$$\Delta_{\text{aDBS dual threshold mode}} = \theta_{\text{cDBS}} - \theta_{\text{aDBS dual threshold mode}}$$

and

$$\Delta_{\text{aDBS single threshold mode}} = \theta_{\text{cDBS}} - \theta_{\text{aDBS single threshold mode}}$$

Where Δ is the mean within-patient change in the objective between the respective aDBS mode and cDBS mode.

7.9.3.1 Voice Handicap Index (VHI)

The VHI has been designed to evaluate the quality-of-life specific to dysphonia. It was developed and validated with patients with a wide range of disorders, including neurological disorders and quantifies the patients' perceptions of the handicap they experience in everyday life due to speech disorders.

The 30-item self-administered questionnaire consists of a 10-item functional subscale, a 10-item emotional subscale, and a 10-item physical subscale. Subjects are asked to read each item and circle one of five response comprising an equal-appearing five-point scale. The scale has the words "never" and "always" anchoring each end and the words "almost never", "sometimes", and "almost always" appearing in between. An "always" response was scored 4 points, a "never" response was scored 0 points, and the remaining options were scored between 1 and 3 points. The score for each subscale is calculated by summing the scores within the subscale and the total score is calculated by summing the scores from the entire questionnaire.

The VHI will be summarized in both "best" and "worst" conditions. A subgroup analysis of this objective will also be performed for those with speech side effects as defined from the MDS-UPDRS question 3.1, score of 2 or greater (mild to severe) in the off medication, off stimulation state at the cDBS Baseline visit.

Missing values

If less than 50% of the items are missing from a subscale, the respective subscale score should be retained with the mean scale score of the items present used to impute a score for the missing items. The total score may be calculated by summing the imputed subscale scores. These imputations will be performed on the Complete Case analysis set.

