9.2. Data Collection

Data collection requirements are summarized in [Table 3](#) below.

Table 3: Study Procedures and Data Collection by Visit

Phase Name		cDBS Baseline Phase		aDBS Setup and Adjustment Phase		aDBS Evaluation Phase		Long-term Follow-up Phase				Extended Access Phase			
Visit Name	Enrollment	LFP Screening	cDBS Baseline	aDBS Setup	Randomization	Visit 1	Visit 2*	Visit 3	Visit 4	Visit 5	Visit 6	Extended Access Visits	Subject Withdrawal / Discontinuation	Unsched. Visit	System Mod.
Informed Consent	X														
Demographics	X														
Medical & surgical history	X														
PD history	X														
C-SSRS (screening)	X														
BDI-II	X														
Pregnancy test	X														
Device information	X														X
Signal Test	X	X		X											
Concomitant medication	X	X	X	X	X	X	X	X	X	X	X	X		X	X
PD medication at visit				X											
PD medication prior to visit		X		X											
PDQ-39			X			X	X	X	X	X	X	X			
EQ-5D-5L			X			X	X	X	X	X	X	X			
MDS-UPDRS IA			X			X	X								
MDS-UPDRS Patient Questionnaire (Part IB & II) Worst condition		X				X	X								

Medtronic Business Restricted

ADAPT-PD MDT19001 Clinical Investigation Plan

Version 5.0

Page 54 of 152

Medtronic

Phase Name		cDBS Baseline Phase		aDBS Setup and Adjustment Phase		aDBS Evaluation Phase		Long-term Follow-up Phase				Extended Access Phase			
Visit Name	Enrollment	LFP Screening	cDBS Baseline	aDBS Setup	Randomization	Visit 1	Visit 2*	Visit 3	Visit 4	Visit 5	Visit 6	Extended Access Visits	Subject Withdrawal / Discontinuation	Unsched. Visit	System Mod.
MDS-UPDRS Patient Questionnaire (Part IB & II) Best condition			X			X	X								
MDS-UPDRS III On stim (cDBS) / On med			X												
MDS-UPDRS III Off stim (cDBS) / Off med		X													
MDS-UPDRS III On stim (aDBS) / On med						X	X								
MDS-UPDRS IV			X			X	X								
PD Home Diary			X			X	X								
C-SSRS (follow-up)						X	X								
VHI Worst condition			X			X	X								
VHI Best condition			X			X	X								
PDSS-2			X			X	X								
BrainSense setup		X		X											
aDBS programming				X									X**		
Physician programming survey				X**										X**	
Patient preference questionnaire						X	X								

Medtronic Business Restricted

This document is electronically controlled

CONFIDENTIAL

056-F275E Rev E Clinical Investigation Plan Template

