9.3. Scheduled Follow-up Visit Windows

Data analyses include follow-up visits, regardless of whether the visit occurs within the window. Therefore, a late visit is preferred over a missed visit but must be accompanied by a deviation report. Follow-up visit windows are listed in [Table 4](#). Should a subject miss a visit or the visit falls outside the pre-specified window, a study deviation must be reported and the original follow-up schedule maintained for subsequent visits.

Table 4: Visit Windows

Visit	Visit ranges
LFP Screening	1-45 days after enrollment
cDBS Baseline	30-45 days after LFP Screening
aDBS Setup	1-45 days after Baseline
aDBS Adjustment	0-60 days after aDBS setup complete
Randomization / Day 0	No greater than 60 days after aDBS setup complete
aDBS Evaluation Visit 1	30-45 days after Day 0
aDBS Evaluation Visit 2*	30-45 days after Evaluation visit 1
Visit 3	45-60 days after Evaluation Visit 2 (or Evaluation Visit 1 if the subject is only configured to one aDBS mode)
Visit 4	45-60 days after Visit 3
Visit 5	90 +/- 14 days after Visit 4
Visit 6	90 +/- 14 days after Visit 5
Extended Access Visits	Every 180 +/- 60 days beginning after Visit 6 and every 6 months thereafter following the previous extended access visit

* If two aDBS modes are set up

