9.5. Prior and Concomitant Medications

All concomitant medications, except for over-the-counter medications and herbal supplements, will be collected for this study. All Parkinson's disease medications will be collected for this study. Subjects' Parkinson's disease medication must be stable at the time of enrollment in the trial through the end of the aDBS Evaluation Phase. During this time, the investigator should make only clinically necessary changes to PD medication.

There are no medication restrictions in the study unless they are investigational and may confound the study results, in which case, prior approval would be needed from Medtronic.

Parkinson's disease medications will be held prior to the LFP Screening and aDBS Setup visits. See [Table 5: PD Medication Off/On Definitions](#).

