9.8.1. LFP Screening Visit

1-45 days after Enrollment

The subject will arrive for the visit off PD medication and on cDBS. Confirm the subject’s PD medication was appropriately withheld as specified in [Table 5](#). If the subject’s PD medications were not appropriately withheld, consider rescheduling the study visit.

Table 5: PD Medication Off/On Definitions

Term	Definition
Off PD Medication	Subject stops taking PD medication(s) for the following time periods prior to a study visit: 
• 72 hours extended-release forms of dopamine agonists• 24 hours regular form of dopamine agonists, controlled release forms of carbidopa/levodopa

Medtronic Business Restricted

	
12 hours regular carbidopa/levodopa, entacapone, rasagiline, selegiline, amantadine
On PD Medication	Optimal motor response to PD medication (“best” On). The clinical symptoms should be stable for at least 10 minutes and both, patient and investigator should agree that the best On of the patient has been reached.
Current PD Medication(s)	Medication the subject is taking for treatment of PD on the day prior to initiating the hold requirements for the Off medication state

Data will be collected, including the following:

- MDS-UPDRS III (Off stim/Off med)
- BrainSense setup and Signal test
- Concomitant medications
- Time of last dose of PD medications taken prior to the visit
- Programming session upload to Medtronic via CDU, with BrainSense data included in the JSON session data report
- Adverse Event and device deficiency assessment

At the start of the visit, the clinician will turn off the subject’s cDBS for approximately 15 minutes.

Following this DBS washout, the trained rater will conduct the MDS-UPDRS III Off med/Off stim assessment.

Next, the clinician should follow the BrainSense setup workflow and perform a Signal Test, using the commercially available Clinician Programmer System, to assess LFP the screening inclusion criterion. The subject must have Alpha - Beta band amplitude $\geq 1.2 \mu\text{Vp}$ detected on at least one (left or right) DBS lead on sensing channels 0-2, 0-3, or 1-3; 8-10, 8-11, or 9-11.

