- MDS-UPDRS Patient Questionnaire (Part IB and II) (worst condition)
- MDS-UPDRS III (On stim (cDBS)/On med) – trained rater
- MDS-UPDRS IV – trained rater
- Collect PD Home Diary and review for completeness
- Concomitant medications
- Collect PKG Watch or confirm it was returned
- AE and device deficiency assessment
- Programming session upload to Medtronic via CDU, with BrainSense data included in the JSON session data report

Medtronic Business Restricted

Following cDBS baseline data collection, the programming session, with BrainSense data included in the JSON session data report, will be uploaded to Medtronic via CDU.

9.9. aDBS Setup and Adjustment Phase

This phase consists of an aDBS Setup Visit and an optional aDBS Adjustment period and ends with randomization. Subjects will be blinded to the aDBS mode during the aDBS Setup and Adjustment Phase. If the blind is broken, document the reasons for unblinding in the subject's source documentation and report as a deviation.

9.9.1. aDBS Setup Visit

1-45 days after cDBS Baseline visit

The aDBS Setup visit may be conducted in one day or may occur over two days, with the final day being no more than 45 days following the cDBS Baseline visit. The aDBS Setup visit should be conducted on sequential days, but when non-sequential days are scheduled there must be no more than 14 days between the visit days.

The subject will arrive for the visit off PD medication and on cDBS. Confirm the subject's PD medication was appropriately withheld as specified in [Table 5](#). If the subject's PD medications were not appropriately withheld, consider rescheduling the study visit.

Data will be collected, including the following:

- Concomitant medications
- Time of last dose of PD medications taken prior to the visit
- PD medication dose given at the visit (if applicable)
- Adverse Event and device deficiency assessment

The clinician should follow the BrainSense setup workflow using the investigational Clinician Programmer System. The subject must have Alpha - Beta band amplitude $\geq 1.2 \mu\text{Vp}$ detected on at least one (left or right) DBS lead on sensing channels 0-2, 0-3, or 1-3; 8-10, 8-11, or 9-11.

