7.9.3.5 Wearable Data

Wearable data will be collected via the PKG Watch as a continuous measure of bradykinesia score (BKS) and dyskinesia score (DKS). A Fluctuation and Dyskinesia score (FDS) will also be derived from the wearable data. The analysis may include reliable data based on day or night on wrist count and all available data.

In addition to the main analysis of wearable data, a subgroup analysis will be performed for those with dyskinesias at least 25% of time. This will be defined from the MDS-UPDRS question 4.1, in the off medication, off stimulation state at the cDBS Baseline visit.

Missing values

Missing data imputation will not be performed with the wearable data.

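### The SAP defines the speech and dyskinesia subgroups from an off-medication, off-stimulation assessment at the cDBS Baseline visit that the protocol never schedules

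*SAP*

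**What the plan says.** SAP 4.4 lists two subgroup analyses that concern this point: wearable data in subjects who have dyskinesia at least 25% of the time, and VHI in subjects with speech side effects. The operational definitions come later in the SAP.

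- **Speech (SAP 7.9.3.1):** MDS-UPDRS item 3.1, "score of 2 or greater (mild to severe) in the off medication, off stimulation state at the cDBS Baseline visit".
- **Dyskinesia (SAP 7.9.3.5):** "This will be defined from the MDS-UPDRS question 4.1, in the off medication, off stimulation state at the cDBS Baseline visit". No qualifying item 4.1 score is printed.

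The protocol schedules these items as follows.

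- **cDBS Baseline visit (Protocol 9.8.3):** "MDS-UPDRS III (On stim (cDBS)/On med) – trained rater" and "MDS-UPDRS IV – trained rater", the latter with no medication or stimulation state.
- **LFP Screening visit (Protocol 9.8.1):** after about 15 minutes with cDBS switched off, "the trained rater will conduct the MDS-UPDRS III Off med/Off stim assessment". In Table 3 (Protocol 9.2) the Part III row headed "Off stim (cDBS) / Off med" is marked only under LFP Screening.
- **Medication holds (Protocol 9.5):** Parkinson's disease "medications will be held prior to the LFP Screening and aDBS Setup visits". The cDBS Baseline visit is not among them.
- **Timing (Protocol 9.3, Table 4):** the cDBS Baseline visit takes place "30-45 days after LFP Screening", so the two are separate visits.

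**The concern.** Each rule combines an item, a state and a visit, and the combination does not occur in the protocol's schedule. Applied exactly, the dyskinesia rule selects nobody, and the speech rule points to a score that does not exist at the named visit.

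A programmer must therefore depart from the written rule. For item 3.1 there are two candidate scores, taken in opposite states at least 30 days apart, and they select on different things: speech with stimulation off, or speech on cDBS. Settling this once outcomes are known is the discretion that an SAP is meant to remove. Both subgroups concern effects (dyskinesia and speech) that Protocol 3.1 says aDBS may reduce.

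**Working it through.** The plan gives no figure to reproduce. The check is a comparison of the two SAP rules with the schedule in Protocol Table 3 and sections 9.5, 9.8.1 to 9.8.3, 9.9.1 and 9.10.

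| Visit | Part III (item 3.1) | Part IV (item 4.1) | PD medication held beforehand |
|---|---|---|---|
| LFP Screening | off stim / off med | not scheduled | yes |
| cDBS Baseline | on stim (cDBS) / on med | scheduled, no state given | no |
| aDBS Setup | not scheduled | not scheduled | yes |
| Evaluation Visits 1 and 2 | on stim (aDBS) / on med | scheduled, no state given | no |

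Off/off Part III is therefore scheduled at one visit, and that visit is not cDBS Baseline. Part IV is scheduled at three visits, none of them labelled off/off. Protocol 9.8.2 also keeps subjects on cDBS throughout the cDBS Baseline period.

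Scheduled scores per subject before aDBS that satisfy each reading of the rules:

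| Reading | Item 3.1 | Item 4.1 |
|---|---|---|
| 1. As written: off/off, cDBS Baseline visit | 0 | 0 |
| 2. Visit read as phase: off/off, cDBS Baseline Phase | 1 (LFP Screening) | 0 |
| 3. State qualifier removed: cDBS Baseline visit | 1 (on/on) | 1 |

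**Dyskinesia.** Readings 1 and 2 both fail, because no Part IV assessment is off/off anywhere in the trial. Only removing the qualifier gives a usable score.

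**Speech.** Reading 2 has support: Protocol 5 and 9.8 place LFP Screening inside the cDBS Baseline Phase, and section 5 lists off-stimulation assessments there. It leaves exactly one matching score, but one taken with stimulation off. Protocol 3.1 treats speech impairment as a stimulation-induced effect, and Table 7 (Protocol 11.4) says that therapy-related events normally resolve once the device is switched off or reprogrammed. A score taken off stimulation is thus a poor marker of a stimulation side effect. Reading 3 uses the state in which SAP 7.9.3.2 already summarizes item 3.1, but an on-stimulation score cannot separate a stimulation effect from the disease.

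**The case against.** The strongest reply is that the intended scores are easy to guess. Part IV is collected only once before aDBS, at the visit the SAP names, so the off/off phrase in 7.9.3.5 looks like wording carried over from 7.9.3.1. Only one off/off item 3.1 score exists in the trial, and it falls in the cDBS Baseline Phase, so changing one word would make the speech rule executable. The argument about the side-effect label rests on a background sentence and an adverse-event definition, neither of which defines this subgroup. SAP 7.11 lets changes that do not alter a principal feature be explained in the study report.

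Part of this stands. The practical ambiguity for dyskinesia is small, the phase reading for speech is plausible, and the label argument shows poor fit, not a contradiction. Printing the item 4.1 score is only a request for missing detail. Relabelling the speech subgroup would also reach the protocol synopsis, Protocol 4.1.4 and SAP 4.4.

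It does not remove the error. Guessing the dyskinesia score means discarding a stated condition. For speech, the rule's visit and state point to two different scores, and the text does not say which part is wrong.

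**Conclusion.** The concern holds. Neither subgroup can be formed from the scheduled data as the SAP is written: there are zero matching scores per subject for each rule. The dyskinesia rule needs correction under any reading; the speech rule needs either its visit or its state corrected.

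The impact is small. Both are descriptive subgroup summaries under the additional objectives, for which SAP 7.9.3 plans no hypothesis testing, in the CC and DSAT sets combined. The primary, secondary and safety analyses do not depend on them. The correction should be made, but it does not threaten the trial's main conclusions.

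The counts assume that assessments are done as scheduled. How many subjects would change speech subgroup between readings 2 and 3 cannot be computed, because the documents give no joint distribution of the two item 3.1 scores.

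**What to change.** Amend the SAP before data freeze.

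1. **SAP 7.9.3.5.** Define the dyskinesia subgroup from item 4.1 at the cDBS Baseline visit, delete the off-medication, off-stimulation qualifier, and print the item 4.1 score that counts as at least 25% of the time.
2. **SAP 7.9.3.1.** Reconcile visit and state in one of two ways:
   - (a) name the off/off item 3.1 score from LFP Screening and relabel the subgroup, for example as speech impairment with stimulation off; or
   - (b) use the on-stimulation, on-medication item 3.1 score from cDBS Baseline, and state that it identifies speech impairment present on cDBS without separating a stimulation effect from disease.

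The cost is two sentences of SAP wording and one printed score, with no new data and no change to visits. Option (a) also needs the label aligned in the protocol synopsis, Protocol 4.1.4 and SAP 4.4; option (b) and the dyskinesia correction do not.
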